5.3.2 Exclusion Criteria

1. Subjects participating in another clinical study that could impact the follow-up or results of this study.

5.4 Subject Enrollment and Inclusion in Analysis

Per ISO 14155, the patient is considered enrolled upon signing and dating an informed consent for participation.

Clinical Investigation Plan

5.5 Total Expected Duration of the Study

The time to complete the MitraClip G4 PMCF study is estimated to be approximately [REDACTED] years.

5.6 Expected Duration of Each Subject's Participation

The final required visit for subjects in the MitraClip EXPAND G4 Study is at [REDACTED] years post-procedure. Therefore, the expected duration of participation for subjects is approximately [REDACTED] months.

5.7 Number of Subjects Required to be Included in the Study

Approximately [REDACTED] subjects will be included in the MitraClip G4 PMCF Study.

5.8 Estimated Time Needed to Select this Number

The estimated time to enroll [REDACTED] patients is about [REDACTED] months.

5.9 Subject Discontinuation

Subjects that are consented and receive a MitraClip G4 implant shall remain in the study until completion of the required follow-up period; however, a subject's participation in any clinical study is voluntary and the subject has the right to withdraw at any time without penalty or loss of benefit. Conceivable reasons for discontinuation may include, but not be limited to, the following:

- Subject death
- Subject voluntary withdrawal
- Subject lost-to follow-up as described below

The Sponsor must be notified of the reason(s) for subject discontinuation. The site will provide this information to the Sponsor. Investigators must also report this to their respective EC as defined by their institution's procedure(s). No additional follow-up will be required or data recorded from subjects once withdrawn, except for the status (deceased/alive). However, if a subject withdraws due to problems related to the device safety or performance, the investigator shall ask for the subject's permission to follow his/her status/condition outside of the clinical study.

Lost-to-Follow-up:

If the subject misses two consecutive scheduled follow up time points and the attempts at contacting the subject are unsuccessful, then the subject is considered lost to follow-up. Site personnel shall make all reasonable efforts to locate and communicate with the subject.

6.0 TREATMENT AND FOLLOW UP ASSESSMENTS

6.1 Pre-treatment

Patients presenting with MR appropriate for treatment with the MitraClip will undergo screening per standard hospital procedure. If a MitraClip procedure is considered appropriate and the patient meets the screening criteria for the study, compliance with MitraClip approved labelling, and not participating in

Clinical Investigation Plan

another study) the site shall obtain consent from the patient. The consent will permit information about the patient to be submitted to the study. No data may be entered into the study unless the informed consent is completed.

6.1.1 Clinical Assessments

Upon completion of Informed Consent, baseline assessment should be conducted per standard of care. Baseline information to be reported into the study include at minimum: medical history, MR severity, KCCQ Score and New York Heart Association (NYHA) Functional Class. If a 6-minute walk test is conducted as standard of care at baseline, these results will be collected in the G4 PMCF Study.

6.1.2 Pre-treatment Imaging

Pre-Treatment Transthoracic Echocardiogram (TTE) and Transesophageal Echocardiogram (TEE) should be conducted per standard of care for a MitraClip Procedure.

6.2 Index Procedure

All Investigators must read and understand the Instructions for Use (IFU) that accompanies the Device. Handling and preparation of the MitraClip G4 System should be in accordance with the IFU. The MitraClip procedure should be conducted in accordance with standard of care practice and approved labelling.

[figure not shown]
6.3 Post-procedure

Post treatment TTE, Clinical Assessments and Laboratory / Clinical Tests should be conducted prior to discharge per standard of care. Post-procedure information (the discharge time point) to be reported for this study include at minimum: Medical Exam and Reporting of Vitals, adverse events, MR severity, KCCQ Score and NYHA Functional Class.

6.4 Subject Follow-up

Follow-up is conducted per standard of care at 30 days and annually through 5 years post-procedure. A 6-month phone call is requested for patients in the study to assess for new adverse event. **Table 1** below outlines the follow-up schedule for this study.

Clinical Investigation Plan

¹Adverse Events to be collected in this study include: all cardiovascular events, device-related complications (as defined in section 4.2), and events classified as MAEs (as defined in section 4.2)

7.0 ADVERSE EVENTS

7.1 Definitions

7.1.1 Adverse Event

An adverse event (AE) is any untoward medical occurrence, unintended disease or injury, or untoward clinical signs (including abnormal laboratory findings) in subjects, users or other persons, whether or not related to the medical device.

As part of ISO14155 Section 3.2, the Adverse Event definition has the following notes:

Note 1: This definition includes events related to the device

Note 2: This definition includes events related to the procedures involved.

Note 3: For users or other persons, this definition is restricted to events related to the MitraClip.

An AE can therefore be any unfavorable and unintended sign (including an abnormal laboratory finding), symptom, or disease temporally associated with the use of a medicinal product, whether or not related to the medicinal product.

7.1.2 Serious Adverse Event

If the AE meets any of the criteria below, it is regarded as a serious adverse event (SAE).

- a) Led to a death,
- b) Led to a serious deterioration in health that either:
 - 1) Resulted in a life-threatening illness or injury, or
 - 2) Resulted in a permanent impairment of a body structure or a body function, or
 - 3) Required in-patient hospitalization or prolongation of existing hospitalization, or
 - 4) Resulted in medical or surgical intervention to prevent life threatening illness or injury or permanent impairment to a body structure or a body function;
 - 5) Chronic disease.
- c) Led to fetal distress, fetal death or a congenital abnormality or birth defect.

Clinical Investigation Plan

A planned hospitalization for pre-existing condition, or a procedure required by the Clinical Study Plan, without a serious deterioration in health, is not considered to be a serious adverse event.

7.1.3 Device Deficiency/Device Malfunction

Device deficiency (DD) is defined as an inadequacy of a medical device related to its identity, quality, durability, reliability, safety or performance, such as malfunction, misuse or use error and inadequate labeling. This includes the failure of the device to meet its performance specifications or otherwise perform as intended. DD information on the MitraClip accessories will also be collecting during G4 PMCF study.

A device malfunction (DM) is the failure of a device to meet its performance specifications or otherwise perform as intended, when used in accordance with the instructions for use or clinical investigation protocol.

7.2 Device Relationship

Determination of whether there is a reasonable possibility that a product or device caused or contributed to an AE is to be **determined by the Investigator** and recorded on the appropriate eCRF form. Determination should be based on assessment of temporal relationships, evidence of alternative etiology, medical/biologic plausibility, and patient condition (pre-existing condition).

7.3 Adverse Event/Device Deficiency/Product Experience Reporting

7.3.1 Adverse Event Reporting

The Investigator will monitor the occurrence of AEs for each subject during the course of the clinical study and report as required by this Protocol in section 7 per AE and SAE definitions. Adverse Events to be reported during this study include: all cardiovascular events, events classified as MAEs (as defined in section 4.2) and device-related complications (as defined in section 4.2). These AEs should be reported starting from the time that the MitraClip delivery system is introduced to the femoral vein through the 5 year follow up visit. In cases with an attempted MitraClip Procedure, but no implant, AEs are only collected through 30 days post attempted procedure.

The investigator should report all required SAEs to the Sponsor as soon as possible but no later than 3 calendar days from the day the study personnel became aware of the event or as per the investigative site's local requirements, if the requirement is more stringent than those outlined. The date the site staff became aware that the event met the criteria of a serious adverse event must be recorded in the source document.

A SAE Notification Form will be made available to allow the investigator to report required SAEs in the event the entry cannot be made in the Electronic Data Capture (EDC) System. This does not replace the EDC reporting system. All information must still be entered in the EDC system as soon as feasible.

Serious adverse events that occurred in the user or persons other than the study subject should not be entered in the EDC system, however need to be reported via the SAE Notification Form.

The Investigator will further report the SAE to the local IRB/EC according to the IRB/EC reporting requirements.

Clinical Investigation Plan

7.3.2 Device Deficiency/Device Malfunction Reporting

All device deficiencies/malfunctions should be reported within the EDC System on the appropriate eCRF form no later than 3 calendar days from the day the study personnel became aware of the event or as per the investigative site's local requirements, if the requirement is more stringent than those outlined. The device, if not implanted or not remaining in the subject, should be returned to Abbott.

Device deficiencies/malfunctions should be reported to the IRB/EC per the investigative site's local requirements. A device deficiency form will be made available to allow the investigator to report device deficiencies/malfunctions in the event that the entry cannot be made in the EDC. This does not replace the EDC reporting system. All information must still be entered in the EDC system as soon as feasible.

7.3.3 Adverse Event Reporting to Country Regulatory Authorities by the Sponsor

The Sponsor will report the SAEs and Device Deficiencies to the country regulatory authority, per local and regional requirements.

8.0 ADJUDICATION OF EVENTS

8.1 The Clinical Events Committee (CEC)

No CEC will be required for this study. Adverse events will be reported per site's assessment.

9.0 STATISTICAL ANALYSIS

[figure not shown]
9.1 Statistical Overview

This is a post-market multicenter study of consecutive consenting patients treated with the MitraClip G4 System at participating centers. The study will enroll a minimum of [REDACTED] subjects to collect clinical evidence for the MitraClip G4 System to characterize the use and outcomes associated with the device. The primary endpoint is Acute Procedural Success (APS). APS is defined as successful implantation of the MitraClip Implant with resulting MR severity of 2+ or less on discharge Echocardiogram (30-day echocardiogram will be used if discharge information is unavailable or uninterpretable). Subjects who die or undergo mitral valve surgery before discharge are considered as an APS failure.

9.2 Analysis Populations

9.3 Sample Size Calculations and Assumptions

Clinical Investigation Plan

9.4 Statistical Analyses

9.4.1 Study Endpoint Analyses

The primary endpoint of the MitraClip G4 PMCF study is Acute Procedural Success (APS). APS is defined as successful implantation of the MitraClip Implant with resulting MR severity of 2+ or less on discharge Echocardiogram (30-day echocardiogram will be used if discharge information is unavailable or uninterpretable). Subjects who die or undergo mitral valve surgery before discharge are considered as an APS failure. This endpoint will be assessed as a proportion of subjects meeting the definition of APS, and tested against a performance goal (PG) of [REDACTED]

The null and alternative hypotheses are stated as:

$$H_0: \text{APS rate} \leq \text{PG}$$

$$H_A: \text{APS rate} > \text{PG}$$

- True APS rate is assumed to be [REDACTED]
- PG is [REDACTED]
- One-sided type I error rate = 0.05

Clinical Investigation Plan

[REDACTED]

[REDACTED]

[REDACTED]

[REDACTED]

[REDACTED]

9.4.2 Clinical Endpoint Analysis

Descriptive analysis will be performed on clinical and safety endpoints defined in Section 4.0. Depending on the type of data (e.g., continuous or categorical), statistical methods described in this section below will be used.

For continuous variables, such as age, means, standard deviations, and 95% confidence intervals for the mean will be calculated.

For binary variables such as sex, counts, percentages, and 95% confidence intervals based on Exact Clopper-Pearson method will be calculated.

For time to event data such as all-cause mortality, Kaplan-Meier analyses will be performed.

For recurrent event data such as recurrent heart failure hospitalizations at pre- and post-procedure, data will be analyzed using annualized event rate in event per patient-year.

9.4.3 Timing of Analysis

The analysis for the PMCF will be conducted when the last subject completes the 30 days visit.

9.4.4 Handling of Multiplicity Issues

There is a single primary endpoint and hence no multiplicity adjustment is needed.

Clinical Investigation Plan

9.4.5 Procedures for Accounting for Missing, Unused or Spurious Data

If Echocardiography assessed MR severity at discharge is unavailable or cannot be assessed, the 30-day value will be used to assess APS. All analyses will be based on available data with missing data excluded. Any unused or spurious data will be noted as appropriate.

9.5 Planned Interim Analysis

No formal interim analyses are planned for this study. Interim study reports with descriptive analysis may be produced for regulatory or reimbursement purposes.

9.6 Success Criteria

The primary endpoint for the PMCF study must be met for the study to be considered successful.

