Subject Visit Schedule	Clinical Visits: Baseline, Discharge, 30 days, 1, 2, 3, 4, 5 years Phone Call: 6 Months
Primary Endpoint	Safety and Effectiveness Acute Procedural Success (APS) defined as successful implantation of the MitraClip device with resulting MR severity of 2+ or less on discharge Echocardiogram (30-day echocardiogram will be used if discharge is unavailable or uninterpretable). Subjects who die or undergo mitral valve surgery before discharge are considered to be an APS failure.
Clinical Endpoints	
 Major Adverse Event (MAE). MAE defined as a composite of all-cause Death, Myocardial Infarction, Stroke, or non-elective CV surgery for device related complications MR Severity (evaluated at Discharge, 30 days, 1 year and 5 years) Device Related Adverse Events (including Mitral valve stenosis, device embolization, Single Leaflet Device Attachment (SLDA), Myocardial perforation, or the need for mitral valve replacement instead of repair due at least in part to the MitraClip procedure or the presence of the MitraClip device)) All-cause mortality Recurrent heart failure hospitalization New York Heart Association (NYHA) functional class improvement Quality of Life (QOL) assessed using the Kansas City Cardiomyopathy Questionnaire (KCCQ) 6 minute walk distance (6MWD)
Inclusion Criteria	
 Subjects scheduled to receive the MitraClip per the current approved indications for use Subjects who give consent for their participation

Clinical Investigation Plan

Exclusion Criteria	
1. Subjects participating in another clinical study that could impact the follow-up or results of this study.

Clinical Investigation Plan

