The Transcatheter Valve Treatment Sentinel Pilot Registry is part of the European Society of Cardiology EuroObservational Research Programme and reports acute and 12-month follow-up results of 628 consecutive patients treated between January 2011 and December 2012 in 25 centers in 8 European countries. Acute procedural success was high (95.4%) with no difference between FMR and DMR patients. Overall, in-hospital mortality was 2.9%. MR reduction to ≤2+ was achieved in 98.2% of patients post-procedure with no difference between MR etiologies. At 1-year, MR was reduced to ≤2+ in 94.0% of patients and 58.6% had mild or no MR, with comparable results obtained for FMR and DMR. The results of the pilot European Sentinel Registry demonstrated that procedural and late mortality was low and lower than expected in such a high-risk cohort, without differences between FMR and DMR. These results confirm long-term benefits previously reported in other real-world registries.

In addition, Abbott has initiated a large scale observational study (█████ patients) in US and EU (EXPAND) to evaluate the safety and performance of the MitraClip NTR/XTR system. The 30 day study outcomes were recently reported in EuroPCR. The acute procedure success rate was 92.9% (962/1035) and 30 day major adverse event rate was very low. MR ≤ 2+ at 30 day was achieved at 90.1% in primary MR patients and 96.3% in secondary MR patients. This study also characterized the baseline mitral valve anatomic features (assessed by the echo core-lab) associated with NTR and XTR clip selection. It was identified that MitraClip XTR (compared to NTR) was more often used in Primary MR in subjects with larger gaps. For secondary MR patients, XTR was used when there was significant leaflet tethering, particularly in the P2/P3 locations.

The totality of post-market clinical evidence supports the use of the MitraClip System for the treatment of MR. The MitraClip G4 PMCF Study will assess the safety and performance of the next generation MitraClip G4 system to confirm that the new design also performs safely and with acceptable outcomes.

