2.2 Rationale for Conducting this Study

This Study will meet PMCF requirements to confirm safety and performance of the next generation MitraClip G4 System. The primary analysis will be conducted using the endpoint of Acute Procedural

²² Puls M, Lubos E, Boekstegers P, von Bardeleben RS, Ouarrak T, Butter C, Zuern CS, Bekeredjian R, Sievert H, Nickenig G, Eggebrecht H, Senges J, Schillinger W. One-Year Outcomes and Predictors of Mortality after MitraClip Therapy in Contemporary Clinical Practice: Results from the German Transcatheter Mitral Valve Interventions Registry. *Eur Heart J.* 2016; 37:703-712.

Clinical Investigation Plan

Success (APS). APS is evaluated by taking into account both safety and performance by capturing safety events related to device failure (re-intervention or death) and performance by the assessment of MR (reduced MR to MR 2+ or less). APS will be evaluated upon discharge from the hospital post procedure. A comparison to the APS rate established by historical clinical data will show the next generation MitraClip G4 System offers the safety and performance expected from MitraClip.

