4.0 STUDY ENDPOINTS

4.1 Primary Endpoint

The primary endpoint is Acute Procedural Success (APS). This is defined as successful implantation of the MitraClip device with resulting MR severity of 2+ or less upon discharge Echocardiogram (30-day echocardiogram will be used if discharge is unavailable or uninterpretable). Subjects who die or undergo mitral valve surgery before discharge are an APS failure

4.2 Clinical Endpoints:

Clinical Endpoints will be assessed at each study time point, all data reported at the corresponding study visit will be included for the study time point.

- Major Adverse Events (MAE): defined as a composite of All-cause Death, Myocardial Infarction, Stroke, or non-elective CV surgery for device related complications
- MR Severity (evaluated at discharge, 30 days, 1 year and 5 years)
- Device Related Adverse Events (including mitral valve stenosis, device embolization, single leaflet device attachment (SLDA), myocardial perforation, or the need for mitral valve replacement instead of repair due at least in part to the MitraClip procedure or the presence of the MitraClip device)
- All-cause mortality
- Recurrent heart failure hospitalization
- Quality of Life (QOL) assessed using the Kansas City Cardiomyopathy Questionnaire (KCCQ)
- New York Heart Association (NYHA) functional class improvement
- 6 minute walk distance (6MWD) (per standard of care)

4.3 Success Criteria:

The MitraClip G4 PMCF Study will be successful if the lower one-sided 95% confidence interval (CI) of the observed APS rate for the study is greater than the Performance Goal (PG) of [REDACTED].

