### 2.3 Primary Endpoint Analysis

For the EXPAND G4 Post Market study Phase II, there will be no hypothesis testing performed. This is a study with descriptive endpoint data in order to collect real world clinical experience of the MitraClip G4 System.

In the MitraClip G4 PMCF study, acute procedural success (APS) will be the only endpoint on which hypothesis testing will be performed. APS is defined as successful implantation of the MitraClip G4 Implant with resulting MR severity of 2+ or less on discharge Echocardiogram (30-day echocardiogram will be used if discharge information is unavailable or uninterpretable). Subjects who die or undergo mitral valve surgery before discharge are considered as an APS failure. This endpoint will be assessed as a proportion of subjects meeting the definition of APS and tested against a performance goal (PG) of 82.8%.

The null and alternative hypotheses are stated as:

$$H_0: \text{APS rate} \leq \text{PG}$$

$$H_A: \text{APS rate} > \text{PG}$$

  

The null hypothesis will be rejected (i.e., successfully passing the PG) if the p-value is calculated to be less than 0.05. The analysis will be performed on the MitraClip G4 PMCF population defined above.

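### Meeting the PMCF acute procedural success goal is said to show safety as well as performance, but the rule counts only death and mitral surgery before discharge, and the SAP defers MAE to 5 years

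*Protocol*

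**What the plan says.** The safety claim stands in two places in Appendix II. The synopsis heads the single primary endpoint "Safety and Effectiveness". Section 2.2 says: "APS is evaluated by taking into account both safety and performance by capturing safety events related to device failure (re-intervention or death"), and adds that the comparison with historical APS "will show the next generation MitraClip G4 System offers the safety and performance expected from MitraClip". Section 2.1 gives the aim of the PMCF study as "to confirm that the new design also performs safely and with acceptable outcomes".

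The success rule rests on APS alone. Appendix II 9.6 states a necessary condition: "The primary endpoint for the PMCF study must be met for the study to be considered successful". Appendix II 4.3 states the sufficient one: "The MitraClip G4 PMCF Study will be successful if the lower one-sided 95% confidence interval (CI) of the observed APS rate for the study" exceeds the performance goal. SAP 2.3 sets that goal at 82.8% and says that "acute procedural success (APS) will be the only endpoint on which hypothesis testing will be performed".

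APS requires successful implantation and MR of 2+ or less at discharge, with the 30-day echocardiogram used when the discharge one is missing or unreadable. On safety, "Subjects who die or undergo mitral valve surgery before discharge are considered as an APS failure".

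MAE (all-cause death, myocardial infarction, stroke, non-elective cardiovascular surgery for device-related complications) is a PMCF clinical endpoint in Appendix II 4.2. It is analysed descriptively, without a goal.

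On timing, SAP 2.6 schedules the PMCF primary endpoint at the last 30-day visit and all remaining endpoints once the PMCF subjects have completed or passed 5 years. Appendix II 9.4.3 says only that the PMCF analysis takes place at the last 30-day visit.

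**The concern.** The study is meant to assess both safety and performance, and a met APS goal is said to deliver both. Most of the plan's own safety composite does not enter the rule. If the plan is followed as written, a success statement that includes safety can issue at 30 days, while the first analysis of MAE that the SAP schedules comes years later. At stake is what the PMCF report may conclude and when. The validity of the APS test itself is not in question.

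**Working it through.** **Inputs.** Goal 82.8%, expected APS 88%, 400 evaluable subjects, exact one-sided 5% test, 90% power, 420 enrolled (SAP 2.3 and 2.4).

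**1. The plan's own figure.** Let X be the number of APS successes among 400. The smallest c with P(X ≥ c | 0.828) < 0.05 is 344, where the probability is 0.0488. The exact one-sided 95% lower limit at 344/400 (86.0%) is 82.82%, just above the goal. P(X ≥ 344 | 0.88) = 0.902, so the stated 90% power reproduces. The rule tolerates 400 − 344 = 56 failures.

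**2. Which MAE components enter the rule.**

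| Event | In MAE | In APS |
|---|---|---|
| Death before discharge | yes | yes |
| Death after discharge | yes | no |
| Mitral valve surgery before discharge | if non-elective and for a device-related complication | yes |
| Mitral valve surgery after discharge | same condition | no |
| Non-mitral cardiovascular surgery | same condition | no |
| Stroke | yes | no |
| Myocardial infarction | yes | no |

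**3. Events outside APS.** The probability of success depends only on the true APS rate. With APS at 88% it is 90.2% whether these events occur in 2%, 10% or 30% of subjects.

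**4. Events inside APS.** Assume a reference in-hospital death rate of 2.7% (the later US registry report in protocol Appendix VI), all other failures fixed, and APS of 88% at that reference.
- Doubled: APS = 88 − 2.7 = 85.3%, P(success) = 0.378.
- Tripled: APS = 88 − 5.4 = 82.6%, P(success) = 0.039.

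More than 56 pre-discharge deaths or mitral operations in 400 (14%) would force failure on their own.

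**5. How many early deaths could fall outside APS.** From the registries in protocol Appendix VI, the share after discharge is 1 − in-hospital rate / 30-day rate:

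| Source | In-hospital | 30-day | Share after discharge | Difference per 400 |
|---|---|---|---|---|
| German registry | 2.4% | 4.5% | 47% | about 8 |
| US registry, initial report | 2.3% | 5.8% | 60% | 14 |
| US registry, later report | 2.7% | 5.2% | 48% | 10 |

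These are rough. The German 2.4% is 18 deaths, which implies 18/0.024 = 750 patients and not the 828 enrolled. The 5.2% comes from the claims-linked part of the US cohort. Two of the three rows are US data, while the PMCF study is European.

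**6. What a 30-day MAE statement would look like.** Two-sided 95% Clopper-Pearson upper limits at n = 420: 13 events (3.1%) give 5.2%; 21 events (5.0%) give 7.5%. The event counts are illustrations, since the documents set no MAE goal.

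**The case against.** The strongest reply is that safety is not left to APS. MAE, all-cause mortality and device-related events are prespecified PMCF endpoints. Binary endpoints get exact 95% intervals (Appendix II 9.4.2, SAP 2.2.2). The PMCF population is already all attempted procedures (SAP 2.1.2). Appendix II 1.1 says adverse events through 5 years will further confirm safety, and Appendix II 2.2 openly names the safety content of APS as re-intervention or death. Any primary endpoint is blind to what it leaves out, so step 3 follows from the definition. All of this stands. It does not remove the sentence in 2.2 that draws a general safety conclusion from APS, and it does not bring MAE into the 30-day report. Appendix II 9.5 and SAP 2.5 allow descriptive interim reports but do not require one.

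A reader might infer four stronger things that the documents do not support:
- *That success is possible whatever the 30-day MAE rate.* Pre-discharge death, and device-related non-elective mitral surgery before discharge, are both MAEs and APS failures, and step 4 shows their effect.
- *That nothing after discharge counts.* The 30-day echocardiogram replaces a missing discharge one, so later MR can decide APS.
- *That the rule barely reacts to in-hospital death.* This needs a true APS well above the plan's 88%. From the predecessor device's 92.9%, a doubling leaves APS at 90.2% and success at 99.7%; from 88% it leaves 38%.
- *That clip embolization or single-leaflet attachment with MR of 2+ or less is scored a success.* APS also requires successful implantation, which the documents do not define closely enough to settle this.

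How a regulator would read a met goal is likewise not something the documents tell us.

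**Conclusion.** The concern holds in a limited form. Appendix II draws a safety conclusion from a rule whose only safety inputs are death and mitral valve surgery before discharge. For stroke, myocardial infarction, non-mitral surgery and post-discharge death or surgery, the verdict carries no information: success probability is 90.2% at any rate of these, given true APS of 88% and 400 evaluable subjects. For the events it does count, the rule is responsive at the planning value (90% to 38% on a doubling of 2.7%, other failures fixed). The registry figures suggest that about half or somewhat more of 30-day deaths could lie outside APS, subject to the caveats in step 5.

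The timing is a separate gap, and it turns a wording problem into a practical one. SAP 2.6 leaves MAE until 5 years, in tension with Appendix II 9.4.3. The test, goal and sample size are not affected.

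**What to change.** Keep the APS test, performance goal and sample size.

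(a) **Limit the conclusion.** In the Appendix II synopsis and 2.2, remove the claim that meeting the APS goal shows overall safety. In 4.3, 9.6 and SAP 2.3, state that a met goal supports acute procedural success only: clip implanted, MR of 2+ or less, and no death or mitral valve surgery before discharge.

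(b) **Time the safety result.** In SAP 2.6, and consistently in Appendix II 9.4.3, schedule 30-day MAE, its components and all-cause death, in all attempted PMCF subjects, for the same 30-day report as APS. Base the 30-day safety statement on the exact upper confidence limit. The planned two-sided 95% Clopper-Pearson interval is enough: with 21 events in 420, the report would say that 30-day MAE is at most 7.5%. No MAE goal, co-primary endpoint or extra alpha is needed.

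The cost is wording in two documents and one additional 30-day table from data already collected. The downside is a narrower success claim, with safety stated as a limit and not as a pass.
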